8. STUDY PROCEDURES/EVALUATIONS

8.1. Clinical Evaluations

Medical History: Will be obtained by interview of the subjects. Subjects will be queried regarding a history of significant – clinically or from the study protocol perspective - medical disorders of the head, eyes, ears, nose, throat, mouth, cardiovascular system, lungs, gastrointestinal tract, liver, pancreas, kidney, nervous system, blood, lymph glands, endocrine system, musculoskeletal system, skin, and genital/reproductive tract. A history of any allergies, cancer, immunodeficiency, psychiatric illness, and substance abuse will be solicited. The collection of medical history information will include a review of vaccine history and plans for vaccinations. All Past influenza vaccinations should be recorded (up to 3 years). Other vaccines history should include at least 30 days before the study and any other study-relevant vaccination received in the past.

Concomitant Medications: All current medications and medications taken within 3 months before Study Day 0 (prescription and over-the-counter drugs) will be included, as well as vitamins and supplements, through 21 days after the last study injection day, unless relevant for chronic background respiratory illness, as per PI judgment, or related to AE or ILI.

Vital signs: blood pressure, oral temperature and pulse will be collected at study visit 1, and as needed at any other study visits Only oral temperature is required to be measured on visit 2. Measurement of oral temperature should be performed with thermometers provided by the study Sponsor. Oral temperature should be measured by keeping the tip of the thermometer under the tongue for sufficient amount of time until the temperature reading stabilizes. In cases when level of oral temperature seems too low the measurement should be repeated and care should be taken to correctly place the tip of the thermometer and to keep it under the tongue for sufficient amount of time (until the temperature stops growing).

Height, weight: These parameters will be measured at Day 0 (Visit 1).

Physical Examination: On Visit 1 standard physical examination should be performed prior to the first study vaccination, but if subject's medical history is known based on medical records, a limited, targeted physical examination may be performed instead of standard scope PE prior to the first study vaccination by a study clinician, however in any case neurologic component of PE and physical examination of head/upper respiratory tract must be performed. On visits other than 1 limited, targeted physical examination may be performed if assessed by investigator as needed.

Reactogenicity Assessments: This will include an assessment of solicited events occurring from the time of each M-001 study vaccination [Day 0 (Visit 1), Day 22 (Visit 2)] through 8 days after the study vaccination (inclusive of vaccination day), which includes an assessment of systemic reactions (Fever; Decreased blood pressure and/or dizziness; Chills and/or sweating; Joint and/or muscle pain; Headache; Nasal congestion, runny nose, phlegm production, rhinitis; Problems with breathing (difficulty breathing, wheezing); General malaise, fatigue, loss of appetite; Itching on body/ pruritus; Swelling/tender lymph nodes; Irritability; Rash; Cough; Sore throat; Stomach problems (abdominal pain, diarrhea, nausea, vomiting)) and local – injection site reactions (Blue spot/ bruising; Induration / Swelling; Redness / Warmth; Itching), Pain/ tenderness

Memory Aids: All subjects will complete a subject memory aid (paper diary) from the time of each study vaccination [Day 0 (Visit 1), Day 22 (Visit 2)] through 8 days after the study vaccination (study vaccination day inclusive). Subject memory aids will be reviewed with the subject for AEs at the site visit following the first study injection, and over the phone after the second study

injection (unless the subject comes to the site for Visit 3). If a subject noted ongoing injection site or systemic reactogenicity on the 7th day following the study injection day, the memory aid will continue to be completed and reviewed until resolved. Subjects will be requested to deliver memory aids filled in after the second vaccination when completed – to the site.

Questionnaires: information on ILI clinical presentation, duration etc. will be collected in the study by study personnel.

8.2. Laboratory Evaluations

Schedules and volumes of clinical laboratory tests and immunogenicity assays are specified in Schedule of events (Table in the Synopsis).

8.2.1. Clinical Laboratory Evaluations

Urine pregnancy tests will be performed by the local or site laboratory within 24 hours prior to each study vaccination (Day 0 (Visit 1) and approximately Day 22 (Visit 2) on all female subjects of childbearing potential. Result must be negative and known prior to randomization on Day 0 (Visit 1) and administration of each study vaccination to be eligible for participation in the study and receipt of each dose of study vaccine.

8.2.2. Nasopharyngeal Samples

For assessment of influenza virus through culture and qRT-PCR, an NP/nasal and throat swab sample will be collected from both nasal passages using two different swab applicators; both swabs are then placed in the same tube of universal transport medium (UTM). Optionally, if NP swab cannot be collected, combined swabs collection from deep nasal (both nostrils) and throat - can be collected instead of NP with three separate applicators, and all three swabs are then placed into the same tube of UTM. Immediately prior to taking the sample, the person performing the procedure will verify the subject's identity and will confirm that the subject number and any other required information on the laboratory request form are those of the subject. Each tube of UTM will be clearly labeled with the self-adhesive bar-coded label provided on the Swab Requisition form that will be applied to the tube immediately before collection of the NP/nasal and throat swab. The subject's identification number and any other required information, the date of sampling, and the date and time of preparation will be clearly documented.

Detailed instructions for the preparation of NP (or combination of nasal and throat swabs) samples are contained in the relevant study manual provided to the sites and relevant study personnel.

8.2.3. Special Assays or Procedures

Cellular (CMI) Studies

Assays to measure T cell responses will be performed by a qualified laboratory. Venous blood samples for isolation of PBMCs will be collected from a subset of cohort 2, immediately prior to the first study vaccination (Day 0, visit 1 in season 2), and approximately 15 days (day of the vaccination inclusive) after the second study vaccination (Day 36, visit 3, season 2).

8.2.4. Specimen Preparation, Handling, and Shipping

8.2.4.1. Instructions for Specimen Preparation, Handling, and Storage

Instructions for specimen preparation, handling, and storage are included in the relevant study manual, as appropriate.

8.2.4.2. Specimen Shipment

Swab samples will be shipped and stored according to applicable regulations and according to the technical requirements aiming at preserving good quality of the material before it is processed for qRT-PCR and (where applicable) for culture confirmation. Swab samples will be analyzed in a qualified laboratory. Details will be contained in the relevant laboratory and study manuals.

Swab samples will be shipped in batches regularly during the course of this study.

Samples for PBMC will be shipped from the sites to the qualified laboratory in a blinded fashion for PBMC isolation and storage before the planned cellular assays take place. Details on shipment and PBMC isolation will be contained in the relevant laboratory and study manuals.

Samples for PBMC will be shipped from sites on ongoing basis aiming at same day or next day delivery, as possible.

9. ASSESSMENT OF SAFETY

9.1. Specification of Safety Parameters

Safety will be assessed by the frequency and severity of:

1. SAEs and NOCIs occurring from the time of the first study vaccination through subjects' participation in the trial.
2. Solicited events – reactogenicity events occurring on the day of each study vaccination through 8 days* after each study vaccination:
**Vaccination day is considered Day 0, with 7 days following (8 days in total)*
 - a) Injection site reactions including pruritus, ecchymosis, erythema, warmth, induration, swelling, pain and tenderness.
 - b) Systemic reactions including fever, feverishness, general malaise, fatigue, loss of appetite, myalgia or arthralgia, decreased blood pressure or dizziness, chills and/or sweating, nasal congestion, runny nose, phlegm production, rhinitis, problems with breathing (difficulty breathing, wheezing), itching on body/ pruritus, swelling/tender lymph nodes, irritability, rash, cough, sore throat, headache and stomach problems (abdominal pain, diarrhea, nausea, vomiting).
3. Unsolicited AEs/SAEs – unsolicited AEs/SAEs occurring from the time of the study vaccination through approximately 22 days after each study vaccination (day of the vaccination inclusive) .

9.2. Safety Assessment

9.2.1. Adverse Events

Adverse Event (AE): International Conference on Harmonisation (ICH) E6 defines an AE as any untoward medical occurrence in a patient or clinical investigation subject administered a pharmaceutical product regardless of its causal relationship to the study treatment. An AE can therefore be any unfavorable and unintended sign, symptom, or disease temporally associated with the use of a medicinal (investigational) product. The occurrence of an AE may come to the attention of study personnel during study visits and interviews of a study recipient presenting for medical care, or upon review by a study monitor.

AEs, will be captured on the appropriate data collection form and electronic case report form (eCRF) as described below in terms of reporting periods. Information to be collected for AEs includes event description, date of onset, licensed study physician's assessment of severity and relationship to study product and considered etiology (if case not related or unlikely related to study product) date of resolution of the event, seriousness and outcome. AEs while on study will be documented appropriately regardless of relationship. AEs will be followed to resolution.

Any medical condition that is present at the time that the subject is screened will be considered as baseline and not reported as an AE. However, if the severity of any pre-existing medical condition increases, it may be recorded as an AE or SAE.

AEs must be graded for severity and assessed for relationship to study product (see definitions below). AEs characterized as intermittent require documentation in the subject's file of onset and duration of each episode. It is up to PI's decision whether the episodes are recorded in the eCRF as separate events or under one event with comment added on the intermittent (or similar) nature of the event. The start and stop date of each reported AE will be recorded on the appropriate data collection form and eCRF within study periods as described below.

•Unsolicited AEs – which do not meet SAE criteria, nor ILI, AESI or NOCI definition should be reported only until ~22 days post each study vaccination, thus - per protocol – such AEs, if they occurred later than 22 days post study vaccination day, should not be recorded in the AE section of the eCRF. They still need to be documented in the subject's study file at the site.

Adverse events of special interest (AESIs) will be captured as SAEs and within the same timelines throughout the subject's participation in the trial. These include new onset of Guillain-Barré Syndrome (GBS), Bell's Palsy, encephalitis / myelitis, optic neuritis, Stevens-Johnson Syndrome, and toxic epidermal necrolysis.

NOCIs should be collected from the time of the first study vaccination throughout the subject's participation in the trial. NOCI is defined as diagnosis of a chronic medical condition where the symptoms commenced or worsened following exposure to the study vaccine. NOCIs meeting criteria of SAE will be recorded as SAE.

Events classified as ILI will not be recorded as AEs/SAEs unless they occur during period from first or second vaccination within 8 days (the vaccination day inclusive) post the respective vaccination or if they meet seriousness criteria - then they are also (in addition to being reported as ILI) reported as SAEs, because ILI cases are to be recorded separately and analyzed for efficacy assessment.

Severity of Event: AEs will be assessed by a licensed study physician using a protocol-defined grading system (see section 9.2.2). For events not included in the protocol-defined grading system, the following guidelines will be used by PI/SI to quantify severity, taking into account subject's medical history, concomitant medications, and baseline values:

- Mild (Grade 1): Events require minimal or no treatment and do not interfere with the subject's daily activities.
- Moderate (Grade 2): Events result in a low level of inconvenience or concern with therapeutic measures. Moderate events may cause some interference with functioning and daily activities.
- Severe (Grade 3): Events interrupt the subject's usual daily activities and may require systemic drug therapy or other treatment. Severe events are usually incapacitating.

Relationship to Study Product: The study physician's assessment of an AE's relationship to study product is part of the documentation process, but it is not a factor in determining what is or is not

reported in the study. If there is any doubt as to whether a clinical observation is an AE, the event should be reported. The relationship to study product must be assessed for AEs using the terms: none, unlikely, possible, probable, certain. In a clinical trial, the study product should be considered as potential suspect. To help assess, the following guidelines are used:

- NONE no evidence of any causal relationship is present
- UNLIKELY There is only little evidence to suggest there may be a causal relationship. Another reasonable explanation for the event exists (medical history, treatment)
- POSSIBLE There is some evidence to suggest a causal relationship but the influence of other factors has been reasonably possible
- PROBABLE There is a reasonable evidence to suspect a causal relationship, and the relevant influence of other factors is less likely.
- CERTAIN - There is clear evidence for the causal relationship, and other reason is very unlikely

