3.2. Study Outcome Measures

3.2.1. Primary Outcome Measures

Safety

- Occurrence of vaccine-related SAEs from the time of the first study vaccination (M-001 or placebo) until end of first passive surveillance period
- Occurrence of NOCIs from the time of the first study vaccination (M-001 or placebo) until end of first passive surveillance period
- Occurrence of solicited injection site and systemic reactogenicity events on the day of each study vaccination through 8 days after each study vaccination (day of the vaccination inclusive)
- Occurrence of unsolicited AEs from the time of first study vaccination through 22 days after each study vaccination (day of the vaccination inclusive)
- Occurrence of all SAEs, regardless of the assessment of relatedness, from the time of receiving the first M-001 study vaccination until end of first passive surveillance period

Clinical Efficacy

- Percentage of either qRT-PCR or culture-confirmed influenza cases in the M-001 experimental group vs. placebo (during period of ≥ 15 days after the second vaccination until epidemiological levels of influenza are low as defined by the medical director) caused by any influenza A or B virus in association with a protocol defined Influenza Like Illness (ILI is defined as symptoms that include one of the respiratory symptoms (sore throat, cough, sputum production, nasal discharge or congestion, wheezing or difficult breathing) and at least one additional systemic symptom [fever (oral temperature $>37.2^{\circ}\text{C}$ for age 50-59, or $>36.7^{\circ}\text{C}$ for age 60 or more, or increased $\geq 1.3^{\circ}\text{C}$ from baseline), headache, myalgia and/or arthralgia, chills, and fatigue (tiredness for at least 12 hours)]. NP or combined nasal and throat swab will be collected from participants who meet the ILI definition within 24 hours from ILI being reported to or identified by study personnel for qRT-PCR analysis of influenza A and/or B virus. PCR confirmed samples will be further analyzed for culture confirmation.

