9.2.2. Reactogenicity

Reactogenicity events are solicited events which are common and considered as possible to occur following administration of this type of vaccine. Reactogenicity (solicited) events are recorded only for 8 days post vaccination (day of the vaccination inclusive). Solicited events (reactogenicity events) which match at least one of the below criteria must be also recorded as AE/SAE or unsolicited AE/SAE:

- symptom/event continues/occurs beyond 7 days post vaccination day (unsolicited AE/SAE)
- reactogenicity symptom/event(s) required medical (i.e. physician's) assistance (AE/SAE)
- reactogenicity symptom/event has been graded by subject or by investigator as severe (AE/SAE)
- oral body temperature of severe grade as per section 9.2.2 Table 8 (AE/SAE)

Per PI/SI's judgment, also cases of symptoms/events occurring within 8 days post vaccination (day of the vaccination inclusive) not meeting the above criteria can be recorded as SAE.

The following Toxicity Grading Scales will be used by PI/SI to grade solicited injection site and systemic (subjective and quantitative) reactions in order to assess whether they qualify as AE/SAE, and if they are severe enough to delay administration of second dose:

Table 5: Injection Site Reactogenicity Grading

Injection Site Reaction	Mild (Grade 1)	Moderate (Grade 2)	Severe (Grade 3)
Pain – experienced without touching the injection site (spontaneous discomfort)	Subject is aware of pain, but it does not interfere with daily activity, and no pain medication is taken	Subject is aware of pain; there is interference with daily activity or it requires repeated use of a non-	Subject is aware of pain, and it prevents daily activity or requires any use of a narcotic pain reliever

Injection Site Reaction	Mild (Grade 1)	Moderate (Grade 2)	Severe (Grade 3)
		narcotic pain reliever for >24 hours	
Tenderness – hurts only when injection site is touched or the arm is moved	The area immediately surrounding the injection site hurts only when touched or with arm motion, and it does not interfere with daily activity	The area immediately surrounding the injection site hurts when touched or with arm motion, and it interferes with daily activity	The area immediately surrounding the injection site hurts when touched or with arm motion, and it prevents daily activity
Pruritus (Itching)	Does not interfere with daily activity	Interferes with daily activity	Prevents daily activity

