9.3. Reporting Procedures

Solicited injection site and systemic reactogenicity events will be documented from the time of each study vaccination (Day 0 (Visit 1) and approximately Day 22 (Visit 2) through 8 days after each study vaccination (day of the vaccination inclusive).

Unsolicited non-serious AEs (excluding NOCIs) will be documented from the time of the study vaccination until 22 days after the study vaccination (day of the vaccination inclusive).

ILI will be documented as AE if occurs within 8 days post vaccination (day of the vaccination inclusive).

SAEs and NOCIs will be documented from the time of the first study vaccination (Day 0 (Visit 1)) through subject’s participation in the trial.

SAEs occurring after the participant completes the study or after early termination need not be reported unless the Investigator believes that the event may have been caused by the study product or a protocol procedure.

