## 5.2 Efficacy Assessment

The assessment of vaccine efficacy will be performed over one flu season and will focus on events which occurred during the flu season in cohorts 1 and 2. Given the surveillance plan, only events which occurred at least 14 days after the second vaccination will be captured.

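### Non-serious illness classified as ILI has no defined AE or ILI record on 20 of the 44 safety-window days, and two protocol rules conflict on whether to record it as an AE

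*Protocol*

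**What the plan says.** Protocol 3.2.1 lists as a primary safety outcome: "Occurrence of unsolicited AEs from the time of first study vaccination through 22 days after each study vaccination", counting the vaccination day.

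Section 9.2.1 then treats ILI separately: "Events classified as ILI will not be recorded as AEs/SAEs unless they occur during period from first or second vaccination within 8 days" of the respective dose, "or if they meet seriousness criteria - then they are also (in addition to being reported as ILI) reported as SAEs". The sentence ends by explaining that ILI is recorded on its own and analysed for efficacy. Section 9.3 repeats the limit: "ILI will be documented as AE if occurs within 8 days post vaccination (day of the vaccination inclusive". Section 9.1 fixes the day count: "Vaccination day is considered Day 0, with 7 days following (8 days in total".

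The separate ILI record starts late. Protocol 7.3 and the schedules of events (Tables 3 and 4) begin ILI surveillance on Day 14 after the second dose. SAP 5.1 dates ILI onset from the same day, and SAP 5.2 says that "only events which occurred at least 14 days after the second vaccination will be captured".

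Section 9.2.2 lists the circumstances in which a solicited event must also be entered as an AE. The first is "symptom/event continues/occurs beyond 7 days post vaccination day (unsolicited AE/SAE". SAP 4.1 repeats this rule.

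**The concern.** The reason for keeping ILI out of the AE record is that it is held elsewhere. Between the end of each 8-day window and Day 14 after dose 2, the plan sets up no such place. The ILI definition is broad: one respiratory symptom plus one systemic symptom is enough. Its components overlap heavily with the events that protocol 2.3.1 lists as seen after M-001, such as nasal congestion, sore throat, cough, headache, myalgia, arthralgia and fever.

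What is at stake is the completeness of a primary safety outcome for the kind of illness that a 22-day window is meant to pick up. There is also the risk that about 85 institutions settle the conflict between 9.2.1 and 9.2.2 in different ways, so that the same illness becomes an AE at one site and not at another.

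**Working it through.** The documents state no figure for this gap, so there is none to reproduce. The count follows from their own day limits, with dose 2 on its planned Day 22.

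| Item | Source | Study days | Number |
|---|---|---|---|
| Unsolicited-AE window, 22 days inclusive per dose | Protocol 3.2.1, 9.3 | 0-21 and 22-43 | 22 + 22 = 44 |
| Non-serious ILI may be an AE | Protocol 9.1, 9.2.1, 9.3 | 0-7 and 22-29 | 8 + 8 = 16 |
| ILI captured as ILI (Day 22 + 14 = Day 36 onward) | Protocol 7.3; SAP 5.1, 5.2 | 36-43 | 8 |
| Neither | by subtraction | 8-21 and 30-35 | 44 - 16 - 8 = 20 |

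The gap is 14 days after dose 1 plus 6 days after dose 2, and 20/44 = 45%.

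Sensitivity to how the limits are read:
- dose 2 on Day 21: 19 of 43
- dose 2 on Day 25 or Day 31: 20 of 44
- AE window read as 22 days after the vaccination day: 20 of 45
- 8-day window read as excluding the vaccination day: 18 of 44
- ILI capture from Day 15 after dose 2: 21 of 44
- one dose only (SAP 5.1 then dates ILI from 35 days after that dose): 22 - 8 = 14 of 22
- SAP Table 2 and SAP 5.1 still hold Season 2 surveillance back to 15 September, a limit that protocol version 5.0 removed. If it applied and fell after Day 43, the gap would be up to 20 + 8 = 28 of 44.

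Now take one illness through the rules: nasal congestion and headache, non-serious, starting on Day 12.
- Under 9.2.1 and 9.3 it meets the ILI definition, lies outside Days 0-7 and is not serious, so it is not an AE.
- Under 7.3 and SAP 5.2 it starts before Day 36, so ILI surveillance does not cover it.
- Under 9.2.2 and SAP 4.1 both symptoms are on the solicited list (protocol 8.1) and occur beyond 7 days, so it must be an unsolicited AE.

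The first and third rules give opposite instructions for the same illness.

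**The case against.** A reader might infer that such illness is recorded nowhere. The documents do not support that. Serious ILI is an SAE throughout (9.2.1, 9.2.4). Diaries collect unsolicited AEs and medications, and the first covers Visit 1 to Visit 2. Interim history is taken at Visit 2 and, in cohort 2, at Visit 3 (7.1, 7.2). Medications are recorded through 21 days after the last dose (6.5), and disease-burden data on respiratory disease or ILI are collected at any time (Tables 3 and 4). Section 9.2.2 requires AE entry outright, and 9.2.1 says that doubtful cases should be reported. Source data will often exist. What is unsettled is entry in the AE data set and its tables.

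It can also be argued that illness before Day 14 after dose 2 is simply not classified as ILI. That is hard to sustain, because 9.2.1 and 9.3 apply the classification to Days 0-7 after each dose, including the first. Section 9.2.4 does pair serious ILI with a parallel ILI record without a Day 14 limit, but this does not help non-serious cases.

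The clause saying that events "which do not meet SAE criteria, nor ILI, AESI or NOCI definition should be reported only until ~22 days post each study vaccination" might be read as a second bar on ILI. It only sets the reporting period for ordinary AEs; the SAEs, AESIs and NOCIs named beside ILI are collected for longer.

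Three further inferences go too far. ILI on Days 14-21 after dose 2 is not lost: it is recorded as ILI and compared by arm (SAP 5.2, 5.4.2), and keeping it out of the AE tables is a defensible choice. A count of missed episodes would need a weekly illness rate, which the documents do not give, and would assume that every site follows 9.2.1 and ignores 9.2.2. And it is too strong to say that an imbalance between arms could not be seen: SAEs, the Day 0-7 events, any AEs entered under 9.2.2, and ILI from Day 14 all remain.

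What stands is the contradiction, and a reason for exclusion that fails in the period at issue.

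**Conclusion.** The point holds for non-serious illness classified as ILI. Under 9.2.1 and 9.3 it has no defined AE or ILI record on 20 of 44 safety-window days (18 to 21 days under other readings of the protocol's limits), while 9.2.2 and SAP 4.1 require the same symptoms to be entered as AEs. Sites cannot follow both rules.

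The consequence is possible under-counting, and uneven recording between sites, of respiratory and systemic illness in the 22-day unsolicited-AE outcome. The rules are the same in both arms, so capture is lowered in both. The size of the loss is unknown: it depends on illness rates and on how sites resolved the conflict. The day count assumes two doses with the second on or near Day 22, and that the ILI classification operates before surveillance starts, as the first-dose exception implies.

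**What to change.** Reconcile protocol 9.2.1 and 9.3 with 9.2.2 so that the ILI exclusion applies only from Day 14 after dose 2, when ILI is captured. Before then, record any non-serious event with onset on Days 0-21 after dose 1 or Days 0-13 after dose 2 as an unsolicited AE, with an ILI-type flag where it meets the definition. Keep the SAE rule for serious ILI as it is.

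In SAP 4.4, present the 22-day AE tables with and without flagged events. Optionally, add ILI episodes with onset on Days 14-21 after dose 2 from the existing ILI data; this needs no double entry. Bring the Season 2 surveillance start in SAP Table 2 and SAP 5.1 into line with protocol version 5.0.

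The cost is protocol and SAP wording plus one eCRF flag, with no extra visits. Common colds will appear in the AE tables of both arms. Cohort 1 (4,055 subjects) was collected before any such change, so pooled tables would mix two capture rules. Show the results by season, as SAP 4.4 already provides, and state the difference in capture.
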